5.3.3. Progression Free Survival

Definition

Progression-free survival (PFS) is measured from randomization until the first documented disease progression or death, whichever occurs first. PFS will be censored on the date of last tumor assessment documenting absence of tumor progression for subjects who have no documented progression and are still alive prior to data cutoff, dropout, lost to follow-up or the initiation of Subsequent anti-cancer treatment. Subjects with no tumor assessments after randomization their PFS will be censored on the date of randomization. PFS is calculated in months as follows:

$$\text{PFS} = (\text{date of PD/death or censoring} - \text{date of randomization} + 1) / (365.25/12).$$

Analysis Methods

The number and percentage of subjects who had a PFS event or were censored will be reported. The Kaplan-Meier method will be used to estimate the distribution of overall PFS for each treatment group, and the median PFS with 95% CI will be provided. In addition, the Kaplan-Meier PFS curve will also be presented by treatment group.

Hazard ratio (Arm B vs. Arm A) and its 95% confidence interval will be presented. In addition, 3, 6, 12-months of PFS rate with 95% CI will be estimated by Kaplan-Meier method and reported for each treatment group.

PFS will also be presented by the subgroups specified in Section 2.4, as appropriate.

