Tumor assessment CT or MRI imaging of all disease sites documented at Screening should be performed using the same methodology throughout the study. Tumor assessments will be performed per RECIST 1.1. For subjects who discontinue treatment for reasons other than progression (eg, adverse event), tumor assessments will continue to be performed until documented disease progression or a new cancer therapy is initiated.			CT or MRI of head, chest, abdomen, and pelvis are required. Include neck if clinically indicated and any other known site of active disease.		X CT or MRI of chest and abdomen (and known sites of active disease) Every 6 weeks (±1 week) for the first 12 months of treatment and every 9 weeks (±1 week) thereafter regardless of treatment delays. Same frequency for all subjects. Imaging timepoints should be calculated from the date of C1D1.							

Table 1: Time and Events Schedule – Safety Run-in, Randomized Arms

Beginning with the implementation of Amendment 7, subjects who continue to derive benefit from atezolizumab treatment, may continue to receive atezolizumab under the supervision of treating investigators in accordance with local regulatory approvals and standard of care guidelines.^{50,51} Data from efficacy and safety evaluations performed according to local regulatory approvals and standard of care guidelines^{50,51} will no longer be collected with the exception of serious adverse events that are to be reported and entered in the Sponsor safety repository.

Assessments	Prescreening (optional)	Screening		Treatment Period (21-day cycles)						EOT (30 +7d after last dose)	Follow-up Period	
				Arm	Cycles 1-3				Cycle 4 and beyond		Pre-PD	Post-PD Survival
					D1 (±3)	D2	D8 (±1)	D15 (±1)				
Day	Any time prior to start of Screening	-56 to -1	-28 to -1									
Laboratory Assessments:												

 - Refer to Inclusion Criterion 6 for specific laboratory values that must be met prior to first dose of study drug administration. - C1D1 laboratory assessments (hematology, chemistry) may be omitted if Screening tests were performed ≤ 7 days prior to the first administration of study drug and the results meet eligibility criteria. After Cycle 1, predose laboratory tests can be conducted up to 72 hours prior to dosing. Laboratory test results must be reviewed by the investigator or qualified designee and found to be acceptable prior to administration of each dose of study drug. 												

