Overlapping toxicities of daratumumab and atezolizumab are not expected. While infusion-related reactions (IRRs) are observed in approximately half of patients treated with daratumumab, IRRs occur in only approximately 1% of patients treated with atezolizumab.

As of 25 May 2018, the Sponsor terminated further enrollment into this study after the third planned Data Monitoring Committee (DMC) review on 23 May 2018. At that time

(n=88, 44 subjects per arm), the DMC determined that there was no observed benefit within the combination treatment arm, daratumumab plus atezolizumab, over atezolizumab alone, and recommended stopping enrollment of the study. In addition, the DMC recommended discontinuation of daratumumab treatment to all active subjects receiving combination therapy (subjects randomized to the combination Arm B, as well as subjects randomized to Arm A who crossed over into Arm B). Although no unexpected imbalances in on-treatment toxicities were observed, the DMC noted a numerical increase in the number of deaths in the combination arm. Therefore, enrollment is discontinued in this study, treatment with daratumumab will be discontinued, and ongoing subjects will be given the option to continue on atezolizumab monotherapy until the subject meets one or more of the treatment discontinuation criteria in Section 10.2. Additionally, Phase 1b expansion to explore the subcutaneous formulation as outlined in Amendment 5 will not be implemented.

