2.1.2. Endpoints

Primary Endpoint

- The primary endpoint is ORR: the proportion of subjects with a partial response (PR) or complete response (CR) as defined by RECIST 1.1

Secondary Endpoints

- Incidence of adverse events
- DoR: the duration from the date of the initial documentation of a response to the date of the first objectively documented evidence of recurrence or progressive disease or death, whichever status is recorded first.
- CBR: the proportion of subjects who achieve disease control (CR, PR, or SD with duration of at least 16 weeks).
- PFS: the duration from the date of randomization to the date of objectively documented progression or death due to any cause, whichever status is recorded first.
- OS: the duration from the date of randomization to the date of death due to any cause.
- Serum daratumumab concentration (C_{min} , C_{max}) and incidence of anti-daratumumab antibodies
- Serum atezolizumab concentration (C_{min} , C_{max}) and incidence of anti-atezolizumab antibodies

Exploratory Endpoints

- ORR_i: the proportion of subjects with a partial response (PR) or complete response (CR) evaluated by irRECIST
- ORR, DoR, CBR, incidence of adverse events, daratumumab and atezolizumab serum concentration and incidence of anti-daratumumab antibodies and anti-atezolizumab antibodies

Refer to Section 9, Study Evaluations for evaluations related to endpoints.

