4. SUBJECT POPULATION

Subjects 18 years and older with advanced or metastatic NSCLC who had at least 2 cycles of standard platinum-based therapy with disease progression or intolerance to therapy will be eligible for this study.

An optional Prescreening informed consent will be offered for the purpose of testing archival tumor tissue to assess PD-L1 status using the SP142 assay (Section 9.1.2) to help determine the likelihood of eligibility for participation in this study. However, final eligibility for study participation will be based on PD-L1 staining on the fresh biopsy required during the Screening Phase, unless the archival tumor sample used in the Prescreening Phase was obtained after completion of the most recent line of therapy with no intervening therapies, and is less than 1 year old. The signing of the main study informed consent and collection of tumor specimen for PD-L1 testing may occur up to 56 days before the first administration of study drug. All other screening procedures must be performed only after PD-L1 results are available, and within 28 days before the first administration of study drug. For subjects who do not meet Inclusion Criterion 5, no further Screening procedures should be performed. For subjects in the randomized phase, treatment should start within 72 hours after randomization.

The inclusion and exclusion criteria for enrolling subjects in this study are described in the following 2 subsections. If there is a question about the inclusion or exclusion criteria below, the investigator must consult with the appropriate Sponsor representative and resolve any issues before enrolling a subject in the study. Waivers are not allowed.

During its review of the study data at the initial interim analysis (40 evaluable subjects), the DMC determined that the study had enrolled a sufficient number of subjects with a PD-L1 score of TC0 and recommended continued enrollment only in subjects in the TC1-3 subgroups. After this DMC recommendation, the sites were notified that only subjects with a PD-L1 score of

TC1-3 will be eligible to enroll in the study, and the protocol was amended to reflect this DMC recommendation (Section 4.1).

For a discussion of the statistical considerations of subject selection, refer to Section 11.2, Sample Size Determination.

After the third data review by the DMC, this study is closed to further enrollment.

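### Read literally, the SAP's no-assessment rule for PFS turns deaths before the first scan into censored observations, against the SAP's own definition and the protocol's

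*SAP*

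**What the plan says.** Protocol 2.1.2 defines the endpoint as "PFS: the duration from the date of randomization to the date of objectively documented progression or death due to any cause", whichever is recorded first. It makes no exception for subjects without a scan. SAP 5.3.3 opens in agreement: "Progression-free survival (PFS) is measured from randomization until the first documented disease progression or death, whichever occurs first".

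Two censoring sentences follow in SAP 5.3.3. The first censors at the last progression-free tumor assessment and is confined to "subjects who have no documented progression and are still alive prior to data cutoff", dropout, loss to follow-up or the start of subsequent anti-cancer treatment. The second reads "Subjects with no tumor assessments after randomization their PFS will be censored on the date of randomization". It has no limit to living subjects and no exception for death.

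The imaging row of protocol Table 1 schedules scans as "Every 6 weeks (±1 week) for the first 12 months of treatment", counted from Cycle 1 Day 1. Protocol Section 4 says that for randomized subjects "treatment should start within 72 hours after randomization". SAP 5.1.2 plans no imputation of missing efficacy values, and SAP 5.3.3 has no sensitivity analysis that would bring these deaths back as events.

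**The concern.** A subject who dies in week 4 has no scan after randomization. Under the definition this is a PFS event at four weeks. Under the second censoring sentence it is a censored time of (0 + 1)/(365.25/12) = 0.03 months, so the subject leaves the risk set before any event has occurred. The worst possible outcome then carries no information. Because the preceding sentence requires the subject to be alive and this one does not, a programmer who follows the text has reason to apply it to deaths.

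The outputs affected are the PFS event counts, Kaplan-Meier curves, medians, 3-, 6- and 12-month rates and hazard ratio. Protocol 3.4 cites predefined censoring rules as one of the safeguards for an open-label design, so the rule should have only one reading. Deaths also matter in this trial: according to Protocol 1.4, at the third review "the DMC noted a numerical increase in the number of deaths in the combination arm".

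**Working it through.** **Plan's own figure.** Neither document states an event target, power or hazard ratio for PFS, so there is no PFS figure to reproduce. The only design figure is 90 subjects for ORR 20% versus 40% at one-sided 0.10. It reproduces at 79% to 80% power with 45 per arm, and this point does not depend on it.

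**Inputs**
- 44 subjects per arm at the third review (Protocol 1.4).
- First scan at week 6 ± 1 from Cycle 1 Day 1 (Table 1), with treatment starting within 72 hours of randomization (Section 4). A subject can therefore be without a scan for up to 7 weeks + 3 days = 7.43 weeks from randomization.
- 6-month OS on atezolizumab of 76% (second line) and 71% (third line or later), and 6-month PFS of 29% and 31%, for TC2/3 or IC2/3 (Table 4). Using these here is an assumption: they come from a PD-L1-selected single-arm study.
- Constant hazards, and no unscheduled scan before an early death (assumptions).

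**Step 1: deaths before the first scan.** Weekly hazard h = −ln(OS at 6 months)/26. The proportion dead by week w is 1 − exp(−w·h).

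| 6-month OS | h per week | dead by week 6 | of 44 | dead by week 7.43 | of 44 |
|---|---|---|---|---|---|
| 76% | 0.01056 | 6.1% | 2.7 | 7.5% | 3.3 |
| 71% | 0.01317 | 7.6% | 3.3 | 9.3% | 4.1 |

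**Step 2: effect on the 3-month PFS rate, equal arms.** Censoring a fraction p on day 1 makes the Kaplan-Meier estimate at 3 months S/(1 − p) instead of S. Take S as the square root of 6-month PFS (constant hazard).
- Second line: S = √0.29 = 53.9%; 53.9/(1 − 0.061) = 57.4%, or 3.5 points too high.
- Third line or later: S = √0.31 = 55.7%; 55.7/(1 − 0.076) = 60.3%, or 4.6 points too high.

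This is about 4 points per arm. A simulation with six-weekly scans and 400,000 subjects per arm gives the same shift and leaves the hazard ratio at 1.00 under either rule.

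**Step 3: effect on the hazard ratio if early deaths differ (assumption).** With the Arm B death hazard doubled throughout, about 5.2 to 6.4 of 44 Arm B subjects are censored on day 1, against 2.7 to 3.3 in Arm A. The simulated hazard ratio (B versus A) falls from 1.26 to 1.20 at the lower death rate and from 1.32 to 1.25 at the higher, a shift of 0.06 to 0.07. Arm B's 3-month PFS is then about 7 to 8 points too high.

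A harsher assumption places the whole Arm B excess before the first scan, with no difference afterwards. With 6% early deaths in each arm the ratio stays at 1.01 under both rules. With 6% versus 12% it is 1.09 with deaths as events and 1.01 with them censored. With 6% versus 18% it is 1.14 and 0.99.

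**The case against.** The literal reading is not the only one. The paragraph begins by making death an event, its formula allows for a death date, and the second sentence may have been meant only to supply a date where the first rule has none. A programmer could follow the definition. That stands: this is an unresolved conflict, and it is not certain that deaths would be dropped. But nothing in the SAP says which sentence prevails.

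A reader might infer from the DMC's remark on deaths that the rule flatters the combination or hides harm. The documents do not support this. They give no death counts by arm and no timing, so an excess before the first scan is not documented. With equal early deaths the hazard ratio does not move. OS (SAP 5.3.4) counts every death from randomization, SAP 6.2 summarizes all deaths, and the DMC had already seen them. Its first-stated finding was that "the DMC determined that there was no observed benefit within the combination treatment arm".

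The shift in the ratio is also small against its precision. With roughly 80 PFS events, the standard error of the log ratio is about 2/√80 = 0.22. The change from 1.26 to 1.20 is ln(1.26/1.20) = 0.05, about a quarter of that. SAP 5.3.3 plans an estimate and interval, with no test.

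Finally, the death rates are borrowed. This trial also enrolled TC0 subjects, a scan may fall in week 5, and Protocol 9.4.1 asks for radiographic confirmation when a subject deteriorates. These points make the counts approximate. They do not resolve the contradiction.

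**Conclusion.** The point holds as an internal contradiction with a measurable consequence under the literal reading. Applied as written, the no-assessment sentence departs from both PFS definitions and removes deaths before the first scan. On constant hazards from Table 4, that is about 3 of 44 subjects per arm by week 6, and 3-month PFS is overstated by about 4 points per arm without any imbalance between arms. Bias in the hazard ratio is conditional on unequal early deaths, which the documents neither report nor rule out. A claim that the analysis favors Arm B would go beyond them. PFS is secondary, and OS and the primary ORR do not change. Severity: should-fix.

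**What to change.** Replace the no-assessment sentence in SAP 5.3.3 with three statements:

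1. *A subject without a post-randomization tumor assessment who has not died, including one who drops out or is lost to follow-up, is censored at randomization.*
2. *A subject who dies before any post-randomization tumor assessment, with no earlier subsequent anti-cancer treatment, dropout or loss to follow-up, has a PFS event on the day of death.*
3. *A subject without an assessment who starts subsequent anti-cancer treatment, drops out or is lost to follow-up before dying stays censored at randomization.*

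The third statement keeps the rule in line with the existing censoring for subsequent treatment and dropout. Without it, a death many months later could become a late PFS event in a subject who was never scanned. Also report, by arm, the number of subjects with no post-randomization assessment and how many of them died. That shows directly whether the rule matters.

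The cost is a short SAP edit, a small change to the PFS derivation and one extra table row. No new data are needed, because death dates are already collected for OS.

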5.3.4. Overall Survival

Definition

Overall survival (OS) is defined as time from date of randomization to date of subject's death from any cause. For subjects who are still alive at the end of study or lost to follow-up, OS will be censored on the date the subjects were last known to be alive. Overall survival is calculated in months as follows:

$$\text{OS} = (\text{date of death or censoring} - \text{date of randomization} + 1) / (365.25/12).$$

Analysis Methods

The number and percentage of subjects who were died or still alive will be reported. The Kaplan-Meier method will be used to estimate the distribution of OS for each treatment group, and the median OS with 95% CI will be provided. In addition, the Kaplan-Meier PFS curve will also be presented by treatment group.

Hazard ratio (Arm B vs. Arm A) and its 95% confidence interval will be presented. In addition, 3, 6, 12-months of OS rate with 95% CI will be estimated by Kaplan-Meier method and reported for each treatment group.

OS will also be presented by the subgroups specified in Section 2.4, as appropriate.

6. SAFETY

The safety profiles of Daratumumab will be evaluated by the incidence of adverse events (AEs), death, laboratory results, vital signs, physical examination findings, ECG results, and ECOG score overtime.

Safety summaries will be provided by treatment received. The severity of AEs and the toxicity of laboratory parameters will be assessed using NCI CTC version 4.03. Adverse events are coded using latest version of MedDRA coding dictionary.

For cross-over subjects, safety data after initiation of cross-over treatment may be summarized separately, as appropriate.

6.1. Adverse Events

Unless otherwise specified, only TEAEs will be summarized.

6.1.1. Treatment Emergent Adverse Events

The following summaries will be provided for all TEAEs:

- An overview of TEAE will be provided, including the incidence of TEAE, serious TEAE, maximal grade of TEAE, treatment discontinuation due to TEAE, , and death due to TEAE.
- A listing of all TEAEs.

In addition, the following summaries will be generated:

- TEAEs by system organ class (SOC) and preferred term (PT)
- TEAEs by SOC, PT, and relationship to study medication
- TEAEs by SOC, PT, and grade 3/4
- Most common (at least 10%) TEAEs by SOC, PT, and grade 3/4
- TEAEs by SOC, PT, and worst grade

- Serious TEAEs by SOC and PT
- Serious TEAEs by SOC, PT, and grade 3/4
- Most common (at least 1%) serious TEAEs by SOC, PT, and grade 3/4

- Grade 3 or 4 TEAEs by SOC and PT
- Grade 3 or 4 TEAEs by SOC, PT, and relationship to study medication

The following summaries of treatment modifications due to TEAEs will be provided:

- Infusion delay due to TEAE by SOC, PT and relationship to study medication

- Infusion skipped due to TEAE by SOC, PT and relationship to study medication
- Infusion interruption due to TEAE by SOC, PT and relationship to study medication
- Infusion rate decreased due to TEAE by SOC, PT and relationship to study medication
- Infusion aborted due to TEAE by SOC, PT and relationship to study medication

In addition, the following summaries will be generated:

- Study drug discontinuation due to TEAEs by SOC, PT, and grade 3/4
- Treatment discontinuation due to TEAEs by PT and grade 3/4
- Death due to TEAEs by PT and grade 3/4

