12.1.3. Severity Criteria

The severity assessment for an adverse event or serious adverse event should be completed using the NCI-CTCAE Version 4.03. Any adverse event or serious adverse event not listed in the NCI-CTCAE Version 4.03 will be graded according to investigator clinical judgment by using the standard grades as follows:

Grade 1 (Mild): Awareness of symptoms that are easily tolerated, causing minimal discomfort and not interfering with everyday activities

Grade 2 (Moderate): Sufficient discomfort is present to cause interference with normal activity

Grade 3 (Severe): Extreme distress, causing significant impairment of functioning or incapacitation. Prevents normal everyday activities

Grade 4: Life-threatening or disabling adverse event

Grade 5: Death related to the adverse event

The investigator should use clinical judgment in assessing the severity of events not directly experienced by the subject (eg, laboratory abnormalities).

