6.1.2. Adverse Events of Clinical Interest

6.1.2.1. Infusion Related Reactions

The incidence of infusion related reactions (IRRs), as flagged on the eCRF, will be presented by SOC, PT, and toxicity grade 3/4. Treatment modifications due to IRRs will also be summarized.

A listing of all IRRs will be provided.

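### The fatal-TEAE table is specified by grade 3/4, and 11 of the 13 graded adverse-event summaries name no grade 5 category

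*SAP*

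**What the plan says.** SAP section 6 grades adverse events on NCI CTC version 4.03. Protocol 12.1.3 also uses NCI-CTCAE 4.03 and adds a five-step scale for events that CTCAE does not list. Its last step is "Grade 5: Death related to the adverse event".

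Among the tables in SAP 6.1.1 is "Death due to TEAEs by PT and grade 3/4". Two others cover only grades 3 and 4 by title; one of them is "Grade 3 or 4 TEAEs by SOC and PT", and the other adds relationship to study medication. For infusion-related reactions, SAP 6.1.2.1 says that incidence "will be presented by SOC, PT, and toxicity grade 3/4", and SAP 6.1.2.3 uses the same words for immune-mediated events.

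Some summaries in SAP 6.1.1 have no upper limit on grade. There is a table of "TEAEs by SOC, PT, and worst grade", and an overview that includes "maximal grade of TEAE, treatment discontinuation due to TEAE, , and death due to TEAE". The section also plans "A listing of all TEAEs". SAP 6.2 summarises all deaths with their primary cause, summarises deaths within 30 days of the last infusion, and lists every subject who died. SAP section 2 has all tables presented by treatment group.

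**The concern.** A fatal-event table split by grades 3 and 4 does not fit its own contents. If the programmer follows the wording, the grade columns have no place for the events that the table exists to show.

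The same split elsewhere affects how severe toxicity is counted. In a table limited to grades 3 and 4, a subject who survives a grade 4 pneumonitis counts as one, and a subject whose only severe event was a fatal pneumonitis counts as zero. Other things equal, an arm whose severe events are more often fatal would look less toxic in that table.

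This deserves care here because Protocol 1.4 reports that "the DMC noted a numerical increase in the number of deaths in the combination arm". Whether any of those deaths came from adverse events, and whether those events were judged related to treatment, is a natural question for the study report.

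**Working it through.** The plan gives no figure to reproduce. The check is a count of the summaries in SAP 6.1.1 to 6.1.2.3 that use a grade, followed by a reading of what each can show.

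**Limited to grades 3 and 4, in SAP 6.1.1 (nine)**
1. All TEAEs
2. Most common TEAEs
3. Serious TEAEs
4. Most common serious TEAEs
5. Grade 3 or 4 TEAEs by system organ class and preferred term
6. The same, by relationship
7. Study drug discontinuation
8. Treatment discontinuation
9. Death

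**Limited to grades 3 and 4, in SAP 6.1.2 (two)**

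10. Infusion-related reactions
11. Immune-mediated events

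**Not capped (two)**

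12. The overview, by maximal grade
13. TEAEs by worst grade

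Total: 9 + 2 + 2 = 13 graded summaries. Capped: 9 + 2 = 11. Not capped: 2.

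**What the cap does.** Items 5 and 6 exclude grade 5 by title. Suppose an arm has *k* subjects, each with one severe event (grade 3 or higher) recorded once at its final grade, and *f* of those events are fatal. The table then counts *k* − *f*. The other nine capped summaries name no grade 5 category. Whether they still count a fatal event in a total column cannot be read from the documents, because the table shells are not in them.

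**What the uncapped summaries recover.** A fatal event appears in the worst-grade table by system organ class and preferred term, and in the overview under maximal grade and under death. Two gaps remain.

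- *Relationship.* The table of all TEAEs by relationship has no grade. The severe-TEAE table by relationship excludes grade 5. The fatal-TEAE table has no relationship. SAP 6.2 gives primary cause of death only. So no named table shows fatal TEAEs by relationship.
- *Events flagged on the case report form.* Infusion-related reactions and immune-mediated events each have one incidence summary with a grade, and it is capped. Beyond that, each has a summary of treatment modifications and a listing.

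**The case against.** The strongest reply is that nothing is lost. Fatal TEAEs remain in the overview, the worst-grade table, the ungraded tables of all and serious TEAEs, and the listings. SAP 6.2 reports every death without a grade filter, and SAP 5.3.4 analyses overall survival by arm. Protocol 11.8 also allows summaries, listings or narratives for subjects who die. This stands as far as the deaths themselves are concerned. It does not supply fatal events by relationship, or a grade 5 category for the two flagged event types.

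A reader might go further and infer that every severity table stops at grade 4, that fatal events drop out of the tables, or that the plan hides the imbalance in deaths. The documents do not support this. Two graded summaries are uncapped, and deaths are shown by arm in several places. The sentence in Protocol 1.4 begins by saying that no unexpected imbalances in on-treatment toxicities were seen. It does not say that the additional deaths were fatal TEAEs. Protocol 12.3.1 keeps disease progression out of the adverse-event terms, so a death from progression need not appear as a fatal TEAE at all.

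It is also fair to object that calling the death table's grade columns empty assumes a layout the documents do not give. A table split by grade 3/4 may carry an any-grade column that counts fatal events by preferred term.

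Finally, the grade list in Protocol 12.1.3 applies to events not listed in CTCAE, and Protocol 12.3.1 records death as the outcome of an adverse event. One could argue that a fatal event keeps a grade of 3 or 4 with a fatal outcome. That would sit badly with Protocol 12.1.3, and the SAP would have to state it. It does not.

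**Conclusion.** The point holds as a specification error of minor severity. The grade split on the fatal-TEAE table is wrong for a table of fatal events. Eleven of 13 graded summaries name no grade 5 category, and two of those exclude fatal events by title, so they undercount subjects with a severe event by the number whose only severe event was fatal. That number cannot be given, because the documents report no count of fatal TEAEs in either arm.

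The conclusion rests on two assumptions: that the tables are programmed as titled, and that fatal events listed in CTCAE are graded 5, as Protocol 12.1.3 grades the unlisted ones. The documents do not reproduce the CTCAE text. The conclusion does not extend to any loss of death data, or to a claim that the planned tables would conceal the difference in deaths that the data monitoring committee noted.

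**What to change.** In SAP 6.1.1, 6.1.2.1 and 6.1.2.3, replace the grade 3/4 and grade 3 or 4 wording with *grade ≥3 (3, 4 and 5 shown separately)*. Change the fatal-event table to *deaths due to TEAEs (grade 5), by preferred term and relationship to study medication*. Presentation by arm is already covered by SAP section 2.

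If the sponsor does intend fatal events to carry a grade of 3 or 4 with a fatal outcome, the SAP should say so and be reconciled with Protocol 12.1.3.

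The cost is SAP wording and table-shell edits. Grade, outcome and relationship are already to be recorded for adverse events, so no new data are needed.
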